9.0 Study Endpoints

The primary endpoints in this study are as follows:

1. Fit evaluation of image-guided PROSE device
 - a) Overall fit parameters (slit lamp)
 - b) Central clearance ordered vs central clearance observed (slit lamp and OCT)
 - c) iTRACE (rotation and decentration)
2. Evaluate ability to dispense after manufacturing one PROSE device with image guided system (YES/NO)
3. PROSE device performance questionnaire (awareness and comfort both graded 0 to 10)

10.0 Procedures Involved

Once a subject has been identified, the initial visit will be scheduled.

See Appendix A "**PROSE/EYEdeal ophthalmic scanning instrument: Schedule of Assessments**" which reviews the list of procedures during each visit and the length of time expected per procedure and per visit.

The testing descriptions are summarized in the table below:

Test	Description
General History and Medications	Participants will be asked questions about their general medical, ocular and medication use histories along with contact lens use history if applicable.
Lens Evaluation	The PROSE device fit will be evaluated via traditional methods utilizing a slit lamp microscope and standard fluorescein dye.
Visual Acuity	The participant's vision in each eye will be measured with a high contrast visual acuity chart. The participant will be asked to cover

TITLE: Pilot study to investigate the feasibility, reliability, and efficiency of utilizing ocular surface optical coherence tomography to automate PROSE fitting

PROTOCOL NUMBER: BFS OCT-01

IRB APPROVED

Jul 14, 2020

NCT04649177

	one eye and read the chart, and this procedure will be repeated for the other eye.
Slit-lamp Examination	The participant's front portion of each eye and PROSE devices will be examined with a lighted microscope. The participant will be asked to place his/her chin on the chinrest and place his/her forehead against the bar and look straight ahead. The instrument's light will be shined onto the eye to visualize the ocular surface for approximately 4 minutes per eye.
Sodium Fluorescein	Sodium fluorescein staining will be used to evaluate ocular surface damage indicated by cell damage or death.
EYEdeal Scanning Ophthalmic Instrument	The EYEdeal Scanning Ophthalmic Instrument is a non-invasive laser product (see 12.0 for more details). The participant will be asked to place his/her chin on the chinrest of the instrument. The forehead is placed against the bar and he/she will be asked to look straight ahead. The investigator will perform a scan of the eye to obtain data relating to the shape of the anterior surface of the eye. Data obtained from these scans at baseline can then be used to manufacture a customized image guided PROSE device.
Optical Coherence Tomography	
Optical Coherence Tomography is an imaging procedure that is used in standard ophthalmic care which uses low-coherence light that can capture resolution down to the micrometer and is commonly used to obtain two and three dimensional images of optical scattering media such as contact lenses and biological tissue.
 
The participant will be asked to place his/her chin on the chinrest of the OCT instrument. The forehead is placed against the bar and he/she will be asked to look straight ahead. The investigator will perform a scan of the eye to obtain an image of the PROSE device on the eye that will allow the measurement of central corneal clearance (the distance between the lens posterior surface and the corneal anterior surface).

TITLE: Pilot study to investigate the feasibility, reliability, and efficiency of utilizing ocular surface optical coherence tomography to automate PROSE fitting

PROTOCOL NUMBER: BFS OCT-01

IRB APPROVED

Jul 14, 2020

NCT04649177

iTRACE Visual Function Analyzer	
iTRACE Visual Function Analyzer is a non-invasive class I laser product which contains two laser diodes, one a Class IIIb laser diode with a 785 nm wavelength, and one a Class IIIa laser diode with a 655 nm wavelength used to image aberrations in the movement of a wavefront of light transmitted through the optical system (the eye). It is a standard instrument used in ophthalmic care.
 
The participant will be asked to place his/her chin on the chinrest of the instrument. The forehead is placed against the bar and he/she will be asked to look straight ahead. The investigator will perform a scan of the eye. The scan data will then be used by the iTRACE software to evaluate the amount of rotation and decentration of the study lens on the eye.

---------------------------------	---

Table 3. Descriptions of tests

11.0 Setting

Subjects will be asked to complete 1-2 study visits at the offices of EYEdeal (Needham, MA) and 2 visits at the clinical facilities at BostonSight.

12.0 Drugs or Devices

PROSE device (BostonSight): The PROSE device is an FDA class II medical device. All rigid lens materials are FDA approved for use in a rigid contact lens, and they are not investigational devices.

Vistane OCT (Zeiss): The Visante OCT is a standard instrument used in ophthalmic clinical practice to image the ocular surface. It is a group 1 Instrument – Per EN ISO 15004–2. Group 1 instruments are ophthalmic instruments for which no potential light hazard exists.

iTRACE Visual Function Analyzer (Tracey Technologies): The iTrace is a 510K exempt medical device used as a tool in ophthalmology clinical practice to measure the refractive, wavefront and corneal topographic data of the human optical system. The FDA has reviewed the premarket notification submission for the Tracey-VFA Visual Function Analyzer (iTrace) and has found this device to be exempt from premarket notification requirements.

The Tracey iTrace Visual Function Analyzer is a Class 1 laser product. It contains two laser diodes:

- 1) Class IIIb laser diode with a 785 nm wavelength, with maximum power of \approx 50 mW and collimated beam with a maximum attenuated

TITLE: Pilot study to investigate the feasibility, reliability, and efficiency of utilizing ocular surface optical coherence tomography to automate PROSE fitting

PROTOCOL NUMBER: BFS OCT-01

IRB APPROVED

Jul 14, 2020

NCT04649177

power of 4.6 mW; and

2) Class IIIa laser diode with a 655 nm wavelength, with maximum power of less than or equal to 2.5mw, and 2mrad beam divergence.

EYEdeal Scanning ophthalmic instrument –

Unlike currently used anterior segment topographers which typically only evaluate corneal contours, the EYEdeal Scanning ophthalmic instrument is concerned with contour measurements of both the sclera and corneal contour. To accomplish this measurement, a slightly modified, off-the-shelf ‘displacement’ type laser distance measuring device is leveraged. This commercial displacement distance measuring instrument functions by emitting a laser beam in one direction and viewing the position of the returned (scattered) light from a position off-axis with a CCD strip detector. In this manner, the instrument is calibrated to determine change in distance based on a change in the position of the returned signal. This laser distance measurement instrument is built into the EYEdeal scanner in such a manner that its laser and returned optical signal are both scanned across the eye via a single axis galvanometer scanner. The scanner moves the location of the measurement beam (the laser spot) from one side of the cornea, up across the apex of the cornea, then down the other side across the full radius of the cornea and well out on to the sclera. This single axis radial scanner oscillates with a triangle wave pattern. As the patient looks into the instrument, the radial scanner is rotated 360 degrees to scan the entire eye. In this manner, radial measurements (‘meridians’) are taken around the axis of the eye every few degrees to completely measure the entire front portion of the eye (anterior segment). This motion can be easily visualized as staring into a large clock face at a short distance. The laser beam scan originates from one end of the minute hand and scans back and forth along the minute hand as the hand sweeps around the clock. Except in this case, the minute hand sweeps the entire 360 degree clock face in 2 to 3 seconds rather than a full hour. Because instrument rotation takes place concurrently with the radial scans, each meridian’s path is somewhat spiral in nature. The total scan time is 2 or 3 seconds and requires just one rotation of the instrument to fully characterize the exposed ocular surface in primary gaze.

Medical Risks and Safety of the EYEdeal Scanning Instrument

Ophthalmic imaging diagnostics such as those to be conducted during this protocol are regarded as non-significant risk (NSR) procedures, and an IRB approved protocol is sufficient (for a properly labeled device) for FDA Investigational Device Exemption (IDE) without FDA review.³ The risks are minimal for testing the imaging instrument. In general, the main risks from laser-based imaging diagnostics are from retinal damage from light exposure to focused (ANSI) Class II or higher laser power levels. However, in this case, the beam is not focused on the retina and is insufficient in power to cause any ocular tissue damage.

TITLE: Pilot study to investigate the feasibility, reliability, and efficiency of utilizing ocular surface optical coherence tomography to automate PROSE fitting

PROTOCOL NUMBER: BFS OCT-01

IRB APPROVED

Jul 14, 2020

NCT04649177

Laser Safety Analysis Summary

To insure that the EYEdeal Scanning instrument meets FDA laser safety requirements and general guidelines for such instruments, EYEdeal Scanning hired “Laser Compliance”, a third party company to perform a detailed analysis of the topology measurement instrument and prepare the attached Laser Safety Report (see Appendix B). Laser Compliance has worked with numerous manufacturers of ophthalmic instruments that incorporate lasers for scanning and surgical procedures, to obtain FDA certification for their products.

Highlights from the attached Laser Safety Report are provided below:

- This instrument as described, does not exceed the published international safety values for the following 3 applicable standards covering laser products, laser eye safety and ophthalmic instrument safety:
 1. The MPE (maximum permissible exposure) for retinal eye safety. IEC 60825-1, edition 2, 2007:03 (now correlated with the ANSI Z136.1)
 2. Corneal & Scleral exposure analysis under the ANSI (American National Standards Institute) Z136.1-2007 E., “American National Standard for the Safe Use of Lasers”.
 3. Retinal exposure analysis specific to ocular instruments under the ISO 15004-2 first edition, 02-2007, “Ophthalmic Instruments - Fundamental requirements and test methods - Part 2: Light Hazard Protection”

[name] confirmed in his attached letter (Appendix B) that the instrument meets all of the above stated safety requirements and states on page 1 of his letter "The EYEdeal Scanner meets all requirements of ISO 15004-2, which applies to the ocular safety of the patient. The safety assessment is summarized in the table below:

Page Break

(From [name] letter)

SUMMARY TABLE OF EYEDEAL SCANNER COMPLIANCE WITH ISO 15004-2:2007

ISO §	Limit	405-nm laser scanned beam	Alignment laser	LED Fixation Target	Combination
5.4.1.1	CW: UV-B Lens	N/A	N/A	N/A	N/A
5.4.1.2	CW: UV-A Lens	N/A	N/A	N/A	N/A
5.4.1.3	CW: Photochemical	SAFE Meets limit with time restriction	N/A	SAFE Meets limit	SAFE Meets limit with time restriction*
5.4.1.4	CW: IR Lens	SAFE	SAFE Emission adhering to ICNIRP	N/A	SAFE

TITLE: Pilot study to investigate the feasibility, reliability, and efficiency of utilizing ocular surface optical coherence tomography to automate PROSE fitting

PROTOCOL NUMBER: BFS OCT-01

IRB APPROVED

Jul 14, 2020

NCT04649177

			Limit!		
5.4.1.5	CW: VIR Lens	SAFE	SAFE	SAFE	SAFE
5.4.1.6	CW: Thermal Retina	SAFE	SAFE	SAFE	SAFE
5.4.2.1	Pulsed: Thermal Retina	SAFE	SAFE	SAFE	SAFE
5.4.2.2	Pulsed: IR Lens	N/A	N/A	N/A	N/A
5.4.2.3	Pulsed: VIR Lens	N/A	N/A	N/A	N/A

[name] concludes "The EYEdal Scanner fully meets the intent of ISO 15004-2: 2007 to protect the patient for a Group 1 device. There is no risk to the patient undergoing topographic assessment by this instrument under any reasonably foreseeable normal use. Nevertheless, I would recommend that the user manual caution the operator not to scan the same eye more than ten scans per day as a conservative precaution against the potential photochemical retinal hazard."

Sterile Preservative-Free Normal Saline:

Preservative Free Normal Saline (0.9% Sodium Chloride solution) is the standard of care solution recommended for use to fill the reservoir in any commercial scleral lens or PROSE scleral lens. Being preservative-free is vital for use in a scleral lens reservoir as preservatives, such as Benzalkonium chloride (BAK), which are commonly found in many ophthalmic products, could have a significant toxic effect on the ocular surface with constant, sustained contact throughout the day.

Flourescein Sodium Strip (Bio Glo, Contacare Ophthalmics and Diagnostics): An ophthalmic dye used as the gold standard in ophthalmic and optometric practices to evaluate devitalized corneal epithelium. Used in the form of a paper strip impregnated with 1.0 mg. of fluorescein sodium. The impregnated strip is moistened with one to two drops of sterile normal saline and applied to the inferior conjunctival fornix.

13.0 Risks to Subjects

This study overall represents a minimal risk to subjects.

TITLE: Pilot study to investigate the feasibility, reliability, and efficiency of utilizing ocular surface optical coherence tomography to automate PROSE fitting

PROTOCOL NUMBER: BFS OCT-01

IRB APPROVED

Jul 14, 2020

NCT04649177

Risk with PROSE devices are those that are already associated with wearing any form of contact lens. All contact lens wearers are at risk for developing an abrasion ('cut' on the eye) during lens application or removal as well as inflammatory and/or infectious complications during lens wear, but there is no added risk of these occurrences by participating in this study.

Adverse events related to ocular surface scanning are not expected due to the safety profile and low scanning energy levels of the EYEdeal Scanning Ophthalmic Instrument. As stipulated above the use of the EYEdeal Scanning Ophthalmic Instrument represents a low risk or "non-significant risk" as stipulated by [name] evaluation.

Each experimental image-guided design will be verified as reasonable by a BostonSight optometrist or ophthalmologist, who will also inspect the finished PROSE device before it is placed on a patient's eye. All trials of experimental PROSE devices will be conducted at BostonSight, according to current standards for placement of trial devices under the supervision of a study doctor.

If a subject experiences an adverse event during the duration of the study, they will be instructed to call the study coordinator who will communicate with the investigators to determine the best course of action. If the subject needs to be seen due to an adverse event, a study investigator will examine them and the customary procedure for management will be followed.

Any adverse event will be treated and followed in keeping with standard medical and optometric practice. Subjects will be given 24-hour contact information for BostonSight providers and instructions to call if they develop new ocular or visual symptoms while participating in this study. All AEs will be evaluated and managed in an appropriate timeframe at an appropriate facility according to the medical judgment of a BostonSight doctor. All BostonSight patients enrolled in the study will have an ongoing relationship and follow-up with BostonSight for the duration of this study and as long as PROSE devices are being worn.

Any adverse effects or unforeseen events relating to the study will be reported directly to the Principal Investigator and to NEIRB.

Following the conclusion of the study the patient will remain under the care of a BostonSight doctor in the traditional sense, for continued evaluations and management while continuing use of a PROSE device, with financial obligations typical to any BostonSight patient.

14.0 Potential Benefits to Subjects

TITLE: Pilot study to investigate the feasibility, reliability, and efficiency of utilizing ocular surface optical coherence tomography to automate PROSE fitting

PROTOCOL NUMBER: BFS OCT-01

IRB APPROVED

Jul 14, 2020

NCT04649177

Subjects may not receive any direct benefit from taking part in this study. If successful, the information obtained from this study could ultimately lead to a reduction in treatment time, and/or an improved design and treatment process. This should potentially decrease cost and increase potential availability to the thousands of patients who can benefit from this new technology.

15.0 Withdrawal of Subjects

Subjects will be withdrawn from the study if they are unable to complete the tasks in the study protocol. In addition, if they experience an adverse event in which the investigator does not feel that the subjects should continue, they will be withdrawn.

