5.0 Number of Subjects

A minimum of 10 current PROSE patients with a primary PROSE treatment indication of an irregular ocular surface/irregular cornea (including but not limited to Keratoconus, Pellucid Marginal Degeneration, Ectasia, Post-Penetrating Keratoplasty, Corneal Scar, Trauma) **AND/OR** ocular surface disease will be enrolled in the study. We can approximate a 10-20% drop-out rate, so we will expect to recruit 12 patients total. The first 10 patients to be eligible and complete the study will be used for data analysis.

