procedures and protections in place at EYEdeal Scanning. Images, video, and data collected on the subjects are maintained on a single computer according to subject identification numbers. The randomly-chosen identification numbers are assigned during the first subject visit and will be stored separately from all other data. The identification numbers can only be linked to the subject via a single password-protected encrypted data file maintained by the PI. Password protected de-identified scan data will be provided to BostonSight on a flash drive or via email.

Data Analysis

The laser scan will produce a series of eye surface height data along each scanned meridian. This data will be processed by an algorithm to determine the shape of the measured meridian. All meridians will then be stitched together to generate a large area topography map and image of the eye. If the data is deemed inadequate or unreliable scans are obtained or optimal scans are not achieved within 1 hour, or if in excess of 10 scans are required, the subject may return on a future date for one additional visit to EYEdeal Scanning, LLC with the same time and scan number constraints.

BostonSight Fitting Visit (no lens for 3 days prior to visit)

Pre-visit calls:

- Contact subject one week before visit to complete COVID-19 travel form
- Contact subject 4 days before visit to remind them not to wear lenses for the next three days.
- Contact subject one day before visit to complete COVID-19 screening form

Visit 4:

- Update medical and ocular history
- Baseline Slit Lamp Biomicroscopy without PROSE device or any contact lens applied in the study eye
- Image-guided PROSE* fit evaluation
 - Slit Lamp Biomicroscopy evaluation of image-guided PROSE device fit in study eye.
 - BCVA (over-refraction as needed) – prescription will be based on current optimized standard PROSE lens
- PROSE device performance questionnaire (after 45 minutes of wear, if able/tolerable)
 - Awareness
 - Comfort
- Post 45 minutes wear time evaluation:

TITLE: Pilot study to investigate the feasibility, reliability, and efficiency of utilizing ocular surface optical coherence tomography to automate PROSE fitting

PROTOCOL NUMBER: BFS OCT-01

IRB APPROVED

Jul 14, 2020

NCT04649177

- Slit Lamp Biomicroscopy evaluation of image-guided PROSE device fit
- Optical Coherence Tomography imaging of central corneal clearance
- iTRACE imaging of lens rotation and decentration

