- Clinician determination if image-guided initial fit could be dispensed after initial fitting visit

**Note: all manufactured PROSE devices will use standard materials and coatings. Lens material and Hydra-PEG coating will match patient's current habitual standard lens.*

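### The first-10-completers rule, read with the withdrawal rules, allows a first-lens failure at Visit 4 to be replaced instead of counted as NO for endpoint 2

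*Protocol*

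**What the plan says.** Four parts of the protocol bear on this.

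- **Analysis set (Section 5.0).** "The first 10 patients to be eligible and complete the study will be used for data analysis". Twelve are to be recruited to allow for 10-20% drop-out. The rule makes no exception by endpoint or by reason for not completing.
- **Withdrawal (Section 15.0).** "Subjects will be withdrawn from the study if they are unable to complete the tasks in the study protocol". The second rule is that "if they experience an adverse event in which the investigator does not feel that the subjects should continue, they will be withdrawn". Neither rule treats events caused by the study lens separately.
- **Visit 4 (Section 8.0).** The image-guided lens is first applied here. The list includes "PROSE device performance questionnaire (after 45 minutes of wear, if able/tolerable", then "Post 45 minutes wear time evaluation" (slit lamp, OCT, iTRACE), and last "Clinician determination if image-guided initial fit could be dispensed after initial fitting visit". The tolerability allowance appears on the questionnaire line only.
- **Endpoint 2 (Section 9.0).** "Evaluate ability to dispense after manufacturing one PROSE device with image guided system (YES/NO".

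The protocol does not define what completing the study means. It also does not say how a subject withdrawn because of the image-guided lens enters endpoint 2.

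**The concern.** Endpoint 2 asks whether the first lens made from the scan could be dispensed. A lens that has to be removed before 45 minutes is an observed failure of that lens, not missing data. If the analysis set depends on completion, and lens failure can itself prevent completion, the set is partly selected on the outcome. The next completer then supplies a result in place of the failure. Any distortion from this path favours the image-guided lens, and with 10 analysed subjects each one carries weight.

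This is more than a detail left to a statistical analysis plan. The protocol itself states who is analysed, so a later plan that counted such a subject would have to depart from Section 5.0.

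**Working it through.** **Step 1. The plan's own figure.** Inputs from Section 5.0: 10 completers, drop-out 10-20%. Formula: n/(1 - d).

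- d = 10%: 10/0.90 = 11.1, so 12
- d = 15%: 10/0.85 = 11.8, so 12
- d = 20%: 10/0.80 = 12.5, so 13

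The stated 12 is reproduced except at the top of the range, where it is one short. The figure matters here only because it shows that replacing non-completers is part of the design.

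**Step 2. Follow one subject whose lens is removed at, say, 20 minutes (a time assumed for illustration).**

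- The questionnaire may be skipped, because its line carries the tolerability allowance.
- The slit lamp, OCT and iTRACE checks after 45 minutes of wear cannot be done as listed, and their line carries no allowance.
- Reading A: the clinician records NO, the visit counts as complete, and the subject is analysed.
- Reading B: the subject could not complete the tasks, or had an adverse event, and is withdrawn under Section 15.0. Section 5.0 then excludes the subject, and another completer takes the place.

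The text permits both readings.

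**Step 3. Size under reading B for one such subject.** Let y be the number of YES results among the 10 analysed. Adding the failure back as NO gives y/11, so the overstatement is

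y/10 - y/11 = y/110.

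| y | Completers only (exact 95% CI) | Failure counted as NO (exact 95% CI) | Overstatement |
|---|---|---|---|
| 10 | 10/10 = 100% (69.2-100%) | 10/11 = 90.9% (58.7-99.8%) | 10/110 = 9.1 points |
| 8 | 8/10 = 80.0% (44.4-97.5%) | 8/11 = 72.7% (39.0-94.0%) | 8/110 = 7.3 points |
| 5 | 5/10 = 50.0% (18.7-81.3%) | 5/11 = 45.5% (16.7-76.6%) | 5/110 = 4.5 points |
| 0 | 0/10 = 0% | 0/11 = 0% | 0 points |

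The intervals are Clopper-Pearson. The comparison adds the failure to the ten, which is what the fix below does. If the failure instead took one of the ten places, the displaced subject's result would decide the difference: 1/10 = 10 points if it was YES, none if it was NO.

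**Step 4. How likely.** The protocol gives no intolerance or adverse-event rate for the image-guided lens, so the expected overstatement cannot be calculated.

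**The case against.** The strongest case is that the protocol already points to reading A. Visit 4 is the last visit, so little remains to withdraw from. The dispense decision needs no lens on the eye, and a lens that cannot be worn is a plain NO. The allowance on the questionnaire line shows that intolerance was foreseen, and it would have little purpose if failing 45 minutes of wear always meant withdrawal. Slit-lamp fit and visual acuity are listed before the wear period. The subjects are established wearers with an optimised fit, and PROSE intolerance is an exclusion (Section 3.0). Each design and finished lens is checked before application, and "All trials of experimental PROSE devices will be conducted at BostonSight" under supervision (Section 13.0). No success threshold is stated for endpoint 2, so no stated decision would change.

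Most of this stands, and it makes the path narrow. It does not close it. Section 15.0 is worded as mandatory, the allowance does not extend to the tests after wear, and completion is undefined. Even with NO recorded, a subject classed as withdrawn falls outside the Section 5.0 set.

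Two stronger readings are tempting and not supported:

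- A reader might take the 10-20% drop-out as one or two lens failures. Two would give 8/10 = 80% against 8/12 = 67%, or 10/10 = 100% against 10/12 = 83%, a gap of 13 to 17 points. That drop-out figure is overall. It covers visits before any image-guided lens exists and says nothing about lens-related withdrawal.
- A reader might infer that the dispense decision is conditional on 45 minutes of wear, or that adverse events could go unreported. The Visit 4 list shows only the order of items, and Section 13.0 requires study-related events to be reported to the principal investigator and the review board.

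**Conclusion.** The concern holds as a narrow ambiguity with a known direction. Followed literally, Sections 5.0 and 15.0 can remove a first-lens failure from primary endpoint 2 and replace it with a completer; they do not require this. The effect is zero if no such withdrawal occurs, or if the clinician records NO and keeps the subject. On the y/11 comparison, one replaced failure overstates the proportion dispensable by at most 9.1 points. The exact intervals are wide and overlap. The result assumes that removal happens after lens application at Visit 4, that the reason is the lens, and that the subject is classed as withdrawn. Withdrawals at the earlier visits are not lens failures and are not affected. Severity is minor, and the change is worth making because it is cheap.

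**What to change.** Add to Section 5.0, with a cross-reference in Section 15.0:

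> If the image-guided lens is removed early, or the subject is withdrawn after lens application at Visit 4 and before the dispense determination, endpoint 2 is recorded as NO and the subject is kept in the endpoint 2 denominator, unless the reason is clearly unrelated to the lens, in which case it is listed with the reason. The first-10-completers set otherwise stands for the fit measurements and questionnaire scores.

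This adds only the failures that would otherwise be lost. It does not bring in an eleventh or twelfth completer. For the same reason it is best applied to subjects fitted before the tenth completion, so that failures are not drawn from a wider pool than successes.

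The cost is two sentences and a cross-reference, plus one judgement by the investigator on whether the reason was unrelated to the lens if such an event occurs. No visits, tests or staff are added. The downside, only if such an event occurs, is a slightly less favourable endpoint 2 result and a denominator that may exceed 10.
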